We designed the PACE clinical study initially to investigate platelet activity in PAD patients and the incidence of major adverse cardiac and limb events after lower extremity revascularization. PACE was set up to investigate the relationship between platelet activity and cardiovascular risk. Many studies suggest the overlapping nature of cardiovascular risk and dementia. Thus, we would like to extend findings that have established the link between heart disease and dementia to platelet activity and dementia. The comprehensive platelet characterization already performed would facilitate our study investigating the association between platelets and cognitive decline in this cohort of patients with established CVD. We will attempt to call all living participants and obtain telephone consent for the additional measure, assess vital status, and perform a validated survey of subclinical cognitive impairment in the PACE cohort with 2 previously validated neuropsychiatric tests that are frequently used in aging studies: TICS and Montreal Cognitive Assessment, MoCA. Both tests can be easily done remotely by trained personnel and are particularly good at detecting early subclinical impairment.

3. Specific Aims

Aim 1. To determine whether preoperative platelet activity measurements are independently associated with short-term cardiovascular events in PAD patients undergoing non-emergent lower extremity revascularization. We will characterize the platelet phenotype in 350 PAD patients before vascular surgery and use Cox proportional hazard models to determine the independent association of the platelet phenotype with risk of cardiovascular events in the first 30 days after surgery.

Aim 2. To determine whether postoperative platelet activity measurements are independently associated with long-term cardiovascular events in patients with established PAD. We will characterize the postoperative platelet phenotype following surgery and use Cox proportional hazards models to determine the independent association of the platelet phenotype with risk of long-term composite of myocardial infarction, stroke, or all-cause mortality with a mean follow-up of 2-years following vascular surgery.

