
There will be a follow-up component of this study that obtains blood and urine following surgery and at their first return visit following surgery. This will allow us to assess the change in platelet activity,

thrombin, coagulation and inflammatory markers during and following the perioperative period. This additional component would consist of a blood collection on postoperative day 2 (+/- 1 day). No more than 60 ml (≈4 table spoons) of blood will be collected at this time point. In addition, a blood collection will be obtained at the subjects' return visit following surgery to the vascular surgeon. No more than 60 ml (≈4 table spoons) of blood will be collected at this time point. The total blood drawn for the follow-up component would be no more than 120ml (8 tablespoons). This blood will be used for the different measurements of platelet activity, thrombin, coagulation and inflammatory markers. Data gathered from this component of the study will help understand the dynamic profile of biomarkers during and following the perioperative period.

Total amount of blood withdrawn will be no more than 180 ml (approximately 12 tablespoons or 40% of a standard blood donation). We believe this amount of blood is small and spread out over a month and therefore patient is at minimal risk. Blood collection at three different time points (before surgery, following surgery while still in the hospital, and at the subjects' first return visit to the vascular surgeon following surgery) will allow us to assess the dynamic change in platelet activity, coagulation and inflammation during the perioperative period. We believe that markers of clotting and bleeding will change during the course of surgery, and that some of these markers may be used to help predict the likelihood of developing a clotting or bleeding event following surgery. The long-term goal is to develop a clinically useful assessment of platelet activity, thrombin generation, coagulation and inflammation for risk stratification that may ultimately serve as a target for therapeutic intervention. The platform proposed will serve as a basis for future research and intervention, and hopefully, will have a great impact on subjects undergoing vascular surgery.

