Blood samples will be assigned a unique code number and stored in the PI's lab without any identifying information other than a code number. The unique code number will not be based on any information that could be used to identify the subject (for example, social security number, initials, birth date, etc.). The master list linking names to code numbers will be kept in a locked file cabinet, separate from all research information placed under double lock and key at the PI's office at NYU Skirball 9th floor. All confidential data will be stored with a unique code as an identifier and will be protected by a double electronic lock. All physical data will be kept under double physical lock. Access to the data will be given to the study personnel only.

Samples will be stored for no more than 10 years following completions of the study. Samples will be used for testing other potential biomarkers in patient plasma and/or serum related to other endpoints not specified in the protocol (e.g. cancer, metabolic disease, etc.). Genetic testing will not be conducted on stored samples. Results of the future research will not be shared with the subjects or their study doctor, and will not become part of the medical records.

Subjects can request for withdrawal of samples at any time by contacting PI [name] in writing. His mailing address is [name]. Withdrawing

Authorization only affects uses and sharing of information after written request has been received, and subject may not withdraw his/her Authorization for uses or disclosures that have previously been made or must continue to complete analyses or report data from the research.

f. After Surgery and Follow Up

Starting on the day of surgery and continuing throughout hospitalization, a physician monitors the patient's course for clinically evident cardiovascular events (MI, stroke, TIA, major bleeding, kidney disease, or any surgical complication). Blood collections and/or ECG's that are performed as part of routine care and/or for study purposes will be recorded and may be used to help ascertain whether a cardiovascular and/or bleeding event has occurred. After hospital discharge, patients will be contacted by telephone (or during their routine clinical follow-up) at 30 days and every 6-month thereafter out to 5-years. At the patients' follow-ups they will be asked questions about their health, lifestyle, and medication use.

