8.1 Data Analysis

All eligible subjects will be assigned a unique identification number upon enrollment in the study. Initial study data will be recorded on a printed form, which will be later converted to an IRB approved electronic database, REDCap. Only study personnel will have access to this database. All potential identifiers will be kept separately in a safe location at the PI's office in NYU Skirball 9th floor, where it will be placed under double lock and key and the PI will have access. After verification of entered data at completion of the study all potential identifiers will be stripped from the database.

Descriptive statistics, including frequency tables, measures of center and variability, and graphical displays will present baseline subject characteristics. Similar analyses will present values of platelet activity measures.

Primary Platelet Activity Measures: LTA and MPA To test the hypothesis that platelet activity measurements are independently associated with 30-day (Aim 1) and long-term (Aim 2) cardiovascular events in patients undergoing lower extremity revascularization we will employ the following analysis. For Aim 1, platelet activity will be measured preoperatively and the main outcome will be 30-day cardiovascular events. For Aim 2, platelet activity will be measured 48 hours postoperatively and the main outcome will be long-term (mean follow-up ~ 2 years) cardiovascular events. We will perform univariate analysis to investigate the association between LTA and MPA platelet activity measures and cardiovascular events. Next, we will examine differences in sociodemographic/clinical factors between participants with and without a cardiovascular event using two-sided tests of proportions for categorical variables (chi-square, Fisher's exact) and t-tests or non-parametric alternatives (e.g., Wilcoxon test) for continuous measures.

The analysis plan outlined above for the primary platelet activity measures will be applied to the set of secondary measures including thrombin. In addition, the analysis plan outlined above for the primary outcome measures will be applied to the secondary outcome measures including major bleeding.

To identify novel mRNA-miRNA target pairs involved in platelet activation, we will computationally inversely correlate miRNA expression with expression of gene targets using established prediction databases

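### Aim 2 does not separate the first 30 days from later follow-up, so a perioperative association could be reported as a long-term one

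*Combined protocol and SAP*

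**What the plan says.** Section 3 poses two questions. Aim 1 uses the preoperative marker and the "risk of cardiovascular events in the first 30 days after surgery". Aim 2 uses the postoperative marker and a Cox model for the "risk of long-term composite of myocardial infarction, stroke, or all-cause mortality with a mean follow-up of 2-years following vascular surgery".

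Section 8.1 restates Aim 2: "For Aim 2, platelet activity will be measured 48 hours postoperatively", and "the main outcome will be long-term (mean follow-up ~ 2 years) cardiovascular events". Section 4.c allows the postoperative draw one day either side of day 2. Section 4.f has participants contacted "at 30 days and every 6-month thereafter out to 5-years".

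The Cox time origin for Aim 2 is not written out. The visible text contains no start at day 30, no exclusion or censoring of earlier events, no division of follow-up time and no check of proportional hazards.

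**The concern.** The aims are presented as a short-term and a long-term question, but the Aim 2 outcome as described includes most of the short-term period. Event rates around revascularization can be much higher than later on, so a small stretch of follow-up may supply a large part of the Aim 2 events. A single hazard ratio then averages two periods in which the marker may behave differently.

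What is at stake is the meaning of a positive Aim 2. The reader could not tell whether the postoperative marker says anything about risk after the perioperative period or only about the weeks just after surgery. That distinction matters for the plan's stated goal of risk stratification.

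**Working it through.** **1. Does the overlap depend on the time origin?** If the clock starts at surgery, all 30 days are shared with Aim 1. If it starts at the day 2 sample, 30 − 2 = 28 days are shared (27 to 29 with the one-day tolerance). The overlap remains under either reading.

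**2. Inputs from the plan.** The planned enrolment is 350 (section 3). Section 8 gives a 0.5 SD difference between participants with and without an event, two-sided 0.025 per co-primary marker, and a 22% 30-day event rate. All three section 8 figures are stated for short-term events. No power or event figure is given for Aim 2.

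The plan's only power figure is 80% with 200 participants. With 44 events and 156 non-events, the standard error is √(1/44 + 1/156) = 0.171 SD. Then 0.5/0.171 − 2.241 ≈ 0.69, which gives about 75% power, or 72% by simulating the Wilcoxon test. That is a separate matter, and the sentence breaks off in the available text. Only its inputs are used here.

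**3. Inputs assumed.** The share of participants with an Aim 2 event by day 30 is set at 5%, 10% or 22%. The later hazard is λ = 0.05 to 0.15 per year. The marker's hazard ratio (HR) is exactly 1.0 after day 30, which is the worst case.

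**4. Effect size.** For a standard normal marker with early event probability 1 − exp(−h·e^(bx)), h and b are solved so that the mean probability is 22% and the event and non-event means differ by 0.5 SD. This gives b = 0.455, or HR = e^0.455 ≈ 1.58 per SD. The same HR is used at all three early rates.

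**5. Share of two-year events from the first 30 days.** Share = p / [p + (1 − p)(1 − exp(−λ(2 − 30/365)))].
- p = 0.05: λ = 0.05 gives 0.05/(0.05 + 0.95 × 0.091) = 37%; λ = 0.15 gives 0.05/(0.05 + 0.95 × 0.250) = 17%.
- p = 0.10: 0.10/(0.10 + 0.90 × 0.091) = 55%, and 0.10/(0.10 + 0.90 × 0.250) = 31%.
- p = 0.22: 0.22/(0.22 + 0.78 × 0.091) = 76%, and 0.22/(0.22 + 0.78 × 0.250) = 53%.

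**6. Simulated Cox analyses.** N = 350, follow-up uniform from 0.1 to 4 years, critical |z| = 2.241. The hazard carries HR 1.58 per SD to day 30 and 1.0 afterwards.

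| Aim 2 events by day 30 (assumed) | Share of two-year events | Single HR significant | HR from day 30 significant |
|---|---|---|---|
| 5% | 17–37% | about 8–14% | about 2–3% |
| 10% | 31–55% | about 22–41% | about 2–3% |
| 22% | 53–76% | about 75–88% | about 2–3% |

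The high end of each range goes with the low later event rate. Repeated runs agree to within a few percentage points; at 5% early events the low end ranged from 7% to 10%. Starting the clock at day 2 lowers the single-HR column by only a few points.

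**7. Weaker early effect.** At HR 1.3 per SD the single-HR column becomes 4–6%, 8–14% and 30–41%. The result is therefore sensitive to both the early effect and the early event rate.

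**The case against.** Several points on the other side stand.

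- **Time origin.** A reader might infer that the plan explicitly counts Aim 2 from surgery. That is the plain reading, but the documents give a follow-up length, not an origin. The firm criticism is that the origin and the handling of early events are unspecified.
- **Different samples.** A reader might infer that Aim 2 simply retests Aim 1. It does not, because Aim 1 uses the preoperative sample and Aim 2 the postoperative one. The problem arises only if the postoperative marker is itself related to early events. Section 4.c expects that some markers may help predict clotting or bleeding after surgery, but the plan gives no figure.
- **The 22%.** A reader might infer that 22% will have an Aim 2 event by day 30 and that early events will dominate. The 22% belongs to short-term cardiovascular events, which the Aims and section 8 do not define and which may be broader than infarction, stroke or death. The last row of the table is an upper case.
- **Cumulative risk is a legitimate target.** A marker that predicts only early events does predict two-year risk from surgery. The all-follow-up HR is not an error; calling it a long-term association is what lacks support.
- **Missing text.** The power paragraph in section 8 is cut off just before 8.1, so the absence of a split is established only for the visible text.

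None of this removes the overlap. It limits how large the effect can be claimed to be, and it argues for adding an analysis rather than replacing one.

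**Conclusion.** The point holds in a limited form. As visible, Aim 2 shares 27 to 30 of Aim 1's 30 days and offers nothing to separate an early association from a later one. Under the worst case of no association after day 30, the chance of a significant Aim 2 result runs from about 8% to 88%, against the nominal 2–3% when only time from day 30 is analysed. Where the study falls in that range depends on three things the documents do not give: the 30-day rate of the Aim 2 composite, the later event rate, and how strongly the postoperative marker relates to early events. Applying 0.025 to Aim 2 is also an assumption.

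The documents do not show that Aim 2 will mislead. They show that, as planned, it could not tell the two situations apart. This is worth correcting because the correction is cheap.

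**What to change.** In Aim 2 and section 8.1:

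1. State the time origin as the postoperative day 2 sample. This also settles events that occur before the draw, for which there is no visible rule.
2. Keep the all-follow-up HR and describe it as cumulative risk.
3. Split follow-up at day 30 and report separate HRs for sample to day 30, and for day 30 onward among participants event-free at day 30.
4. Describe an association as long-term only on the basis of the HR from day 30 onward.

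The cost is wording and one extra model term. A 30-day contact is already scheduled, so no new data are needed. The later HR will rest on fewer events, have a wider interval, and apply only to participants event-free at day 30.

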Aim 3. To investigate mRNA-microRNA co-expression profiles in patients with and without elevated platelet activity measurements. We will establish the relationship between differentially expressed microRNAs and their target mRNAs related to platelet activity and thus identify new diagnostic markers and potential therapeutic targets of increased platelet activity.

Aim 4. To investigate whether the platelet phenotype of patients with PAD associates with measures of cognitive impairment. We will contact participants enrolled in PACE to conduct a screening test for cognitive function via telephone and/or video-call using the MoCA and/or TICS tests. We will correlate these measures with already collected platelet activity measures.

4. Research Design

a. Recruitment

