Following the interview and signed informed consent, subjects will have their blood drawn, and will be asked to provide a urine sample prior to surgery. Blood will be obtained from the patient using standard aseptic phlebotomy techniques. Blood will be collected from an arterial line placed for surgery (if available) or at the time of the intravenous line being placed for surgery or using a standard technique of blood drawing. A brief description of the standard technique follows: after cleansing of the venipuncture site with an alcohol wipe and removal of excess alcohol with sterile gauze, a tourniquet will be applied to the patient's bicep region. A 19G or 21G butterfly needle will be inserted into the antecubital vein, the tourniquet will be removed, and free-flowing blood will be collected with minimal trauma and stasis. The needle will be removed when blood collection is complete and sufficient pressure will be applied using sterile gauze at the puncture site until cessation of bleeding. A sterile band-aid will be applied to cover the venipuncture site. For each patient, no more than 60 ml (≈4 table spoons) of blood will be collected in gold (serum separator tube) top, lavender (EDTA anticoagulant) top, green (heparin), blue (sodium citrate anticoagulant) top and Pax gene tubes. Approximately 40 cc of blood will be used for the different measurements of platelet function, inflammation, coagulation and other biomarkers of cardiovascular risk and approximately 20 cc of blood will be used to purify platelet RNA, whole blood RNA and DNA and then stored in -80C for the RNA, microRNA, and DNA profiling. The samples will be placed in the PI's lab at NYU New Science Building- Cardiology 7th floor without any identifying information other than a code number. The code number will not be based on any information that could be used to identify the subject (for example, social security number, initials, birth date, etc). The master list linking names to code numbers will be kept in a locked file cabinet, separate from all research information in the PI's office at NYU Skirball 9th floor and will be accessed by the PI. The urine specimen will be collected to measure abnormalities in thrombosis, hemostasis and inflammation as well. At the end of the patient recruitment and measurement of platelet function (probably within 4 years time), based on ones level of platelet activity, thrombin generation, coagulation and inflammation we will measure RNA, microRNA, and DNA in patients with different phenotypes of vascular disease, markers of thrombosis/hemostasis, and events from the stored specimens.

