The blood specimen will be analyzed upon completion of the study for mRNA, microRNA, and DNA profiling. We will perform detailed molecular profile study, describing genetic arrays with different phenotypes associated with platelet activity. We will be looking at specific transcripts associated with thrombotic and/or bleeding outcomes and different cardiovascular diseases. Platelet-rich plasma (PRP) will be isolated for platelet purification and subsequent genetic analysis will be performed. We will be analyzing those with high and low levels of platelet activity and other cardiovascular biomarkers as well as those with clotting/no clotting or bleeding/no bleeding. Biomarkers of cardiovascular disease will be shared as per NIH. The samples will be stored in the PI's lab, NYU New Science Building- Cardiology 7th floor, without any identifying information other than a unique code number. The code number will not be based on any information that could be used to identify the subject (for example, social security number, initials, birth date, etc.). The master list linking names to code numbers will be kept in a locked file cabinet, separate from all research information. Biomarker testing is separate from genetic testing. Genetic information will not be disclosed to anyone, including the participants and their physicians. Positive test result can be an indication that the individual may be predisposed to high platelet activity associated with peripheral vascular disease. There is no need for independent testing since patients are already diagnosed with this condition. No tests other than authorized shall be performed on the biological sample. Samples shall be destroyed at the end of the testing process.

e. Future Sample Storage

All patients will be offered an option to have their blood stored for future processing. If a patient does not agree to store his/her blood for future tests not related to this study, then his/her blood will be destroyed after all planned laboratory tests have been performed.

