Power and sample size analysis was performed to investigate appropriate sample size for evaluating platelet activity markers in subjects with cardiovascular disease CVD versus age- and sex matched controls. The study is powered based on the analysis of association between platelet activity and cardiovascular events. Based on published and preliminary data, we expect the 30-day event rate to be 22%. The relationship between platelet activity and short-term cardiovascular events will be assessed using 2 co-primary measures: LTA and MPA. Based on preliminary data, LTA levels have skewed distribution and MPA levels are normally distributed. Consider a transformation (e.g. log- or Box-Cox) on LTA measures that achieves Normality. With 200 participants, two-sided Wilcoxon test will have 80% power at the 0.025 significance level to detect an association between platelet reactivity and short-term events corresponding to a 0.5*standard deviation difference in platelet

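### Aim 3 compares expression between elevated and non-elevated (high/low) platelet-activity groups, although LTA and MPA are continuous; regression on the measured values would recover information at almost no cost

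*Combined protocol and SAP*

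**What the plan says.** Section 3, Aim 3, is framed as a comparison of two groups: "To investigate mRNA-microRNA co-expression profiles in patients with and without elevated platelet activity measurements". Its next step depends on that comparison: "We will establish the relationship between differentially expressed microRNAs and their target mRNAs related to platelet activity". The intended product is to "thus identify new diagnostic markers and potential therapeutic targets of increased platelet activity".

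Section 4.d (Genetic Profiling) repeats the grouping: "We will be analyzing those with high and low levels of platelet activity and other cardiovascular biomarkers". It adds groups defined by whether a clotting or bleeding event occurred. Section 4.c (Methods) says that the choice of assays follows recruitment: "based on ones level of platelet activity, thrombin generation, coagulation and inflammation we will measure RNA, microRNA, and DNA in patients with different phenotypes". The same sentence also brings in disease phenotype and events.

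Section 8 (Statistical Analysis) treats the two main platelet measures as continuous. It says that "LTA levels have skewed distribution and MPA levels are normally distributed" and contemplates a log or Box-Cox transformation of LTA. The only method given for Aim 3, in section 8.1, is that "we will computationally inversely correlate miRNA expression with expression of gene targets using established prediction databases".

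The available text gives no cut-off for elevated, no choice of marker for Aim 3, no number of patients to be profiled and no rule for patients in the middle of the distribution.

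**The concern.** Grouping a continuous measure treats a patient just above the cut-off like one far above it, and a patient just below it like one far below. For a transcript that rises steadily with platelet activity, that discards usable signal. Aim 3 first has to find differentially expressed microRNAs, then links them to target mRNAs, so a transcript missed at the first step is lost to the second. The section 8.1 correlation does not help, because it relates expression to expression and platelet activity does not enter it as a measured value. Aim 4, by contrast, plans to correlate cognitive measures with the platelet measures, so the protocol does not group throughout.

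The stake is power in an exploratory aim. The samples and marker values will already exist, so the loss is avoidable without further assays.

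**Working it through.** **Inputs from the documents.** Two-group contrast (Aim 3; section 4.d). Continuous markers, MPA Normal and LTA skewed (section 8). Planned cohort of 350 (Aim 1: "We will characterize the platelet phenotype in 350 PAD patients before vascular surgery"). The plan states no sample size, power or cut-off for Aim 3, so there is no figure of its own to reproduce.

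**Assumptions.** Marker X is standard Normal, after transformation for LTA. Transcript Y is linear in X with correlation ρ. The ρ values below are illustrative and do not come from the documents.

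**Case A: everyone assayed is split at a cut-off.** With upper share p, cut-off z and Normal density φ, the efficiency relative to regression on X is φ(z)² / [p(1 − p)].

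- Median: 0.3989² / 0.25 = 0.637
- Top third vs rest: 0.3636² / 0.2222 = 0.595
- Top quarter vs rest: 0.3178² / 0.1875 = 0.539

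Applied to 350 patients, these are worth 223, 208 and 189 patients analysed on the measured value (350 × 0.6366, 0.5949 and 0.5386).

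**Case B: only the two outer groups are assayed.** With tail share p on each side, the tail mean is m = φ(z)/p and the mean square in the tails is 1 + z·m. The efficiency of the group contrast, relative to regression on X in the same samples, is m² / (1 + z·m).

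- Outer thirds: 1.091² / (1 + 0.431 × 1.091) = 0.81
- Outer quarters: 1.271² / (1 + 0.674 × 1.271) = 0.87
- Outer tenths: 1.755² / (1 + 1.282 × 1.755) = 0.95

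**What this means for power.** Simulated power for one transcript, 350 enrolled, 5,000 replicates. The 0.001 level stands in for a stricter threshold, since the plan gives none.

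| Analysis | ρ = 0.15, α 0.05 | ρ = 0.15, α 0.001 | ρ = 0.20, α 0.05 | ρ = 0.20, α 0.001 |
|---|---|---|---|---|
| All assayed, measured value | 81% | 32% | 97% | 68% |
| All assayed, median split | 62% | 14% | 85% | 39% |
| All assayed, top quarter vs rest | 54% | 11% | 79% | 30% |
| Outer quarters only (174 samples), two groups | 71% | 22% | 92% | 53% |
| Outer quarters only (174 samples), measured value | 77% | 27% | 95% | 62% |
| Random half (175 samples), measured value | 50% | 10% | 76% | 26% |

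The measured-value analysis has more power than the group analysis in both designs. The gain is large if everyone assayed is split and modest if only the extremes are assayed. The last three rows also show that assaying extremes is efficient per sample, so it is the grouping, not the selection, that loses information.

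**The case against.** **The plan may not be the one with the large loss.** If profiling is limited to extremes, which section 4.c permits, the design is efficient and the avoidable loss is only about 5% to 19%. This stands, and the size has to be given as two ranges. It does not remove the gain.

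**The efficiency formula concerns one transcript and one marker, not co-expression.** This is correct. The formula bears on the differential-expression step that Aim 3 requires first, and says nothing about the microRNA-to-target correlation.

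**The text may be incomplete.** The power statement in section 8 stops mid-sentence, and the Aim 3 paragraph in section 8.1 has no closing punctuation. A fuller model may have been lost in extraction, so the point is limited to the available text.

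**A reader might infer that Aim 3 will overstate diagnostic accuracy.** The documents do not support this. The aim speaks of diagnostic markers but plans no AUC, sensitivity or specificity. Inflation also requires leaving out the middle: the wording of Aim 3 excludes nobody, and section 4.d leaves the question open. Only in that event would the risk arise. At an assumed ρ of 0.3 to 0.5, the AUC is 0.635 to 0.730 for a median split of all patients, but 0.711 to 0.840 in outer quarters alone. Weighting could not repair that, because patients with no chance of being profiled carry no data to weight.

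**A reader might also infer that regression on the marker is automatically unbiased because selection is on the regressor.** That would hold if platelet activity alone decided who is profiled. Sections 4.c and 4.d also name thrombin generation, coagulation, inflammation and events, which may be related to expression at a given level of LTA or MPA.

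**Conclusion.** The point holds as a low-severity improvement to an exploratory aim. As written, Aim 3 compares two groups on continuous measures, and the available text contains no model of expression on the measured value. The two-group contrast loses about 36% to 46% of the information if all assayed patients are split between the median and the top quarter (1 − 0.637 to 1 − 0.539). It loses about 5% to 19% if only the outer tenths to outer thirds are assayed. Which range applies cannot be determined, because the cut-off, the marker and the patients to be profiled are not stated.

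These figures rest on a Normal marker after transformation and a linear relation with expression; the powers also rest on the assumed correlations. The result shows neither that Aim 3 is underpowered, since no Aim 3 sample size or effect is given, nor that any accuracy claim is planned or wrong.

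**What to change.** 1. State who will be profiled: which marker, which cut-offs or sampling fractions, how many patients, and whether the middle of the distribution is included.
2. For whoever is profiled, make the primary differential-expression analysis a regression of each transcript on transformed LTA or MPA as a continuous variable. Keep the high/low contrast as a descriptive or secondary analysis.
3. Record every variable used to choose samples, including other biomarkers and clotting or bleeding events, and adjust for them or weight by the selection probabilities. Do not assume an unbiased slope.
4. Check linearity with a spline, and say that the check covers only the sampled part of the marker range.
5. If the middle is not profiled, describe the results as discovery and report no diagnostic accuracy. An accuracy estimate would need patients from the whole marker range.

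Items 1 to 4 change wording and analysis only and need no extra assays. The downside is the linearity assumption, which cannot be checked in an unsampled middle. An accuracy estimate, if one were wanted and the middle had been left out, would require further profiling.
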